10.7.2 Individual Adverse events Analyses

Individual rates of each adverse event category contributing to the primary and secondary safety endpoints will be examined using the binomial estimate including the two-sided 95% exact confidence intervals.

10.7.3 Additional Pre-Specified Safety Analyses

The appropriate statistical methods will be utilized to evaluate the additional pre-specified analyses listed in section 6.6 including:

- Kaplan-Meier method for time to event analyses
- Binomial estimates and exact confidence intervals for rates
- Descriptive statistics such as mean, standard deviation, median, interquartile range, minimum and maximum for continuous data and frequency and percentage for discrete data.

10.7.4 Effectiveness Endpoint Analyses

The primary effectiveness endpoint of overall shock effectiveness for spontaneous discrete episodes of VT/VF will be examined using the binomial estimate including the one-sided 95% lower exact confidence bound.

³⁰ Peto method for standard error estimate

The secondary endpoint of first shock effectiveness for acute and spontaneous discrete episodes of VT/VF will be examined using the binomial estimate including the one-sided 95% lower exact confidence bound. If the difference in first shock effectiveness rate for the acute and spontaneous episodes is statistically significant at a 0.05 significant level using a chi-square test then separate analyses will be presented for first shock efficacy of induced and spontaneous episodes.

10.7.5 Additional Pre-Specified Effectiveness Analyses

Descriptive statistics such as mean, standard deviation, median, and ranges for continuous data and frequency and percentage for discrete data will be utilized to analyze the additional pre-specified effectiveness data listed in section 10.5.

10.7.6 Baseline and Procedural Experience Analyses

Demographics and baseline clinical variables, including but not limited to relevant descriptors from the medical history, risk factors, co-morbidities, NYHA functional class for heart failure and medications will be summarized for the cohort of subjects enrolled in this study. Continuous variables will be summarized as means, standard deviations, medians and ranges. Categorical variables will be summarized as frequencies or percentages. A summary of the eligibility status of enrolled subjects will be performed.

Also outcomes related to the S-ICD System procedure such as, but not limited to, type of anaesthesia, implant duration, use of fluoroscopy or X-ray for system positioning, length of hospital stay and use of dual zone programming and rate cut-offs will be summarized.

10.7.7 Poolability Analysis

Poolability analysis for both primary safety and effectiveness endpoint will be analyzed.

The log-rank test will be utilized to determine any relevant difference in Kaplan-Meier curves with the primary safety endpoint. A chi-square test will be used to analyze the difference in overall shock effectiveness rate for the primary effectiveness endpoint.

10.7.8 Sensitivity Analysis

Every effort will be utilized to minimize missing data. The denominator for each variable and all analyses will be presented in each report. The number of subjects withdrawing from the study will be presented with the corresponding time of discontinuation. [REDACTED]

[REDACTED]

[REDACTED]

[REDACTED]

[REDACTED]

[REDACTED]

[REDACTED]

[REDACTED]

10.7.9 Subgroup Analysis

[REDACTED]

[REDACTED]

[REDACTED]

[REDACTED]

[REDACTED]

[REDACTED]

[REDACTED]

10.8 Reports

At a minimum, an annual report to the FDA will be provided by the sponsor summarizing the following: enrollment and implant status, device usage including out of service devices, protocol deviations, baseline characteristics, procedural data, reported adverse events, unanticipated adverse device effects, deaths, number of spontaneous episodes of VT/VF and corresponding conversion results.

10.9 Additional Pre-specified Analyses

Descriptive statistics will be used to further characterize the performance of the S-ICD System. Additional pre-specified analyses will include, but are not limited to, the

additional safety analyses listed in section 6.6, additional effectiveness analyses listed in section 10.5 and the following:

- Clinical Indications for implant
- Demographics and baseline characteristics of the implant population
- Whether subject was a candidate for a TV-ICD and reason for S-ICD System implantation
- Type of anesthesia/analgesia
- Management of antiplatelet and anticoagulation medications during implant
- Use of medical imaging during implant
- Programmed settings
- Use of dual zone programming and rate cutoffs

10.10 Other Statistical Considerations

11. ADVERSE EVENTS

11.1 Adverse event Reporting

All adverse events related to the S-ICD System must be reported to the sponsor. An adverse event should not be reported if it was considered a pre-existing medical condition or a non-cardiovascular related event clearly unrelated to the S-ICD System or procedure. In addition, events in which there is no untoward clinical occurrence in the subject should not be reported.

Investigators must report clinical events to the sponsor as described in **Table 12**.

Table 12: Investigator Reporting Timelines for Deaths and Clinical Events

Event Type	Reporting Time
Death and all SA(D)Es	As soon as possible, but no later than 2 working days after becoming aware
Reportable Adverse Device Effect	As soon as possible, but no later than 10 working days after becoming aware
Device Deficiencies	As soon as possible, but no later than 1 working day after becoming aware

Examples of events that do not require reporting include:

- Follow-up or exacerbation/worsening of pre-existing conditions including: diabetes, cancer, allergies, osteoporosis, arthritis, heart failure, etc.
- New medical conditions unrelated to the S-ICD System including: diabetes, cancer, allergies, osteoporosis, arthritis, etc.
- Physical trauma or injury unrelated to the S-ICD System including: musculoskeletal injuries, joint aches and pains, tendonitis, bursitis or burns from external causes.
- Rotation of the pulse generator in which the subject experiences no discomfort or other untoward clinical occurrence.
- Device explant or replacement in the absence of any untoward medical occurrence, including normal battery depletions
- Adverse events or sequelae related to a different procedure or separate medical device, such as a concomitant pacemaker or abandoned/extracted lead
- Normal battery depletion
- Inability to implant the device (e.g., due to high DFTs)

If it is unclear whether or not an event should be reported, investigators should conservatively report the event.

11.2 Adverse event Definitions

Adverse event – Any untoward medical occurrence in a subject. This definition does not imply that there is a relationship between the event and the system under investigation.

Adverse Device Effect - Any untoward or unintended response to a medical device. This definition includes any event resulting from insufficiencies or inadequacies in the instructions for use or deployment of the device. It also includes any event that is a result of user error.

Serious Adverse Event – An adverse event that:

- Led to a death;

- Led to a serious deterioration in the health of the subject that:
 - resulted in a life-threatening illness or injury,
 - resulted in a permanent impairment of a body structure or a body function,
 - required in-subject hospitalization or prolongation of existing hospitalization,
 - resulted in medical or surgical intervention to prevent permanent impairment to body structure or a body function;
- Led to fetal distress, fetal death or a congenital abnormality or birth defect.

Serious Adverse Device Effect- An adverse device effect that has resulted in any of the consequences characteristic of a serious adverse event or that might have led to any of these consequences if suitable action had not been taken or intervention had not been made or if circumstances had been less opportune.

Observation – An adverse event that does not result in invasive intervention. Examples of such non-invasive intervention include, system reprogramming, antibiotic treatment of pocket infection, or change in medications.

Complication – An adverse event that results in permanent loss of device function,³¹ invasive intervention or death.

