7.5 Adverse events and Spontaneous Episode Classification

Complications and treated spontaneous episodes will be preliminarily classified by investigational sites and reviewed for final adjudication by a Clinical Events Committee (CEC).

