11.3 Classification of Adverse events

All adverse events will be categorized as observations or complications based on the intervention required to resolve the adverse event. A complication is an adverse event that results in permanent loss of device function, invasive intervention or death.

All adverse events will also be classified by type based on the cause of the adverse event. The following definitions for adverse event types will be used:

- Type I: Caused by a component of the S-ICD System, including the pulse generator, electrode, electrode insertion tool or programmer

³¹ *Permanent loss of device function* refers to: 1) the permanent loss of shock therapy and/or post shock pacing; 2) permanent loss of appropriate sensing in all available sensing configurations (oversensing that results in persistent inappropriate shocks or undersensing that could lead to undetected arrhythmias). Loss of device function includes programming the PG permanently off or temporarily off in advance of an explant/revision.

- Type II: Other adverse events not specifically caused by a component of the S-ICD System, but would not have occurred in the absence of the implanted S-ICD System
- Type III: Caused by a change in the subject's condition
- Type IV: Pre-existing medical condition or occurred while the subject was not enrolled

Adverse events will typically be labelled and categorized according to the clinical presentation, including device malfunctions.

In the event of a subject death, the S-ICD System should be interrogated, removed from the subject, and returned to BSC for analysis. The data related to the death should be recorded in the database in a timely fashion. A detailed death letter should also be provided to the sponsor.

In the event that the SQ-RX pulse generator or Q-TRAK subcutaneous electrode cannot be removed, the SQ-RX pulse generator should be interrogated prior to interment. Note that failure to remove the S-ICD System from a deceased subject prior to cremation may cause the battery to explode when the device is exposed to extreme temperatures.

All subject deaths will be reported by the sponsor to the appropriate regulatory agencies.

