Appendix A Acronyms and Definitions

bpm	beats per minute
CEC	Clinical Events Committee
CFR	Code of Federal Regulations
Adverse event	Any untoward medical occurrence in a subject
CRF	Case Report Form
Complication	A complication is an adverse event that results in permanent loss of device function, invasive intervention or death.
ECG	Electrocardiogram
EIT	Electrode Insertion Tool
FCC	Federal Communications Commission
ERI	Elective Replacement Indicator
FCE	Field Clinical Engineer
FDA	US Food and Drug Administration
GCP	Good Clinical Practice
GLP	Good Laboratory Practice
ICD	Implantable Defibrillator
ICF	Informed Consent Form
IRB	Institutional Review Board
J	Joules
LVEF	Left Ventricular Ejection Fraction
ms	Millisecond
N/A	Not Applicable
NNT	Number Needed to Treat
NR	Not Required
Normal Battery Depletion	A pulse generator that is not associated with a complaint and has reached its elective replacement indicator(s) with implant time that meets or exceeds the nominal (50th percentile) predicted longevity at default (labelled) programmable settings OR with implant time exceeding 75% of the expected longevity using the longevity calculation tool available at time of product introduction, calculated using the device's actual use conditions and programmable settings
NSR	Normal Sinus Rhythm
NYHA	New York Heart Association
Observation	Observations are adverse events that do not result in invasive interventions. Examples are reprogramming or medication change.
OUS	Outside the United States
PCMCIA	Personal Computer Memory Card International Association
PCr	Serum (Plasma) Creatinine Level
Permanent Loss of Device Function	Refers to: 1) the permanent loss of shock therapy and/or post shock pacing; 2) permanent loss of appropriate sensing in all available sensing configurations (oversensing that results in persistent inappropriate shocks or undersensing that could lead to undetected arrhythmias). Loss of device function includes programming the PG

	permanently off or temporarily off in advance of an explant/revision.
PMA	Premarket Approval
ppm	pulses per minute
RF	Radio Frequency
SAS	Statistical Analysis System
Spontaneous Episode	Any arrhythmia that is stored by the SQ-RX pulse generator
SVT	Supraventricular Tachycardia
Time to Therapy	Time to therapy is defined as the interval starting 2000ms after the last induction artifact (the time of the post induction refractory) and ending at the onset of the shock deflection on the ECG recording.

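### Observation and Complication overlap when a device-caused event ends with the generator permanently programmed off without surgery, and CEC review of site-labelled observations is not described

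*Combined protocol and SAP*

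**What the plan says.** Section 11.2 defines an observation as "An adverse event that does not result in invasive intervention" and illustrates it: "Examples of such non-invasive intervention include, system reprogramming, antibiotic treatment of pocket infection, or change in medications". Appendix A repeats both elements: "Observations are adverse events that do not result in invasive interventions" and "Examples are reprogramming or medication change".

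Section 11.3 makes the two categories an either/or choice: "All adverse events will be categorized as observations or complications based on the intervention required to resolve the adverse event". The next sentence gives the other definition: "A complication is an adverse event that results in permanent loss of device function, invasive intervention or death". Footnote 31, attached to the Complication entry in 11.2, explains loss of function: "Loss of device function includes programming the PG permanently off or temporarily off in advance of an explant/revision". Footnotes 9 and 27, attached to the primary safety endpoint in 6.1 and 10.1, say the same.

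On adjudication, 7.5 begins: "Complications and treated spontaneous episodes will be preliminarily classified by investigational sites", and then provides for final adjudication by the Clinical Events Committee (CEC). Section 19.1 describes the committee's remit more broadly, as important endpoints and relevant adverse events reported by investigators, and leaves procedures to a charter.

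The primary safety endpoint (6.1, 10.1) is the rate of freedom from Type I complications at 60 months (1800 days). Under 10.1.2 it passes if the one-sided 95% lower bound of the Kaplan-Meier estimate, with the Peto standard error, exceeds 85.0%.

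**The concern.** The two categories are meant to be exclusive, but their definitions are not complements. A complication has three alternative criteria, and an observation rules out only one of them. An event that meets either of the other two without surgery falls in both.

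The clearest case is a device-caused adverse event resolved by switching the generator off for good. Judged by the intervention, this is reprogramming, which is the plan's own example of an observation. Judged by the outcome, it is permanent loss of function and so a complication. Two sites could label the same event differently, and each could cite the protocol.

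The label matters because the primary safety analysis counts Type I complications. If a complication is filed as an observation and nobody corrects it, the subject is treated as complication-free. That error can only move the estimate toward passing. The rule has to be applied alike at up to 150 sites (7.1) over 60 months.

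**Working it through.** **Step 1. Apply each definition to the possible outcomes of a Type I adverse event.**

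| Outcome | Observation (11.2, Appendix A) | Complication (11.2, 11.3) |
|---|---|---|
| Any invasive intervention | No | Yes |
| Generator switched off temporarily before explant or revision | No, surgery follows | Yes |
| Generator switched off permanently, no surgery | Yes | Yes |
| Death, no invasive intervention | Yes | Yes |
| Settings changed, function kept, no surgery | Yes | No |

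Rows three and four meet both definitions. In 11.3 the sorting sentence points row three toward observation and the next sentence points it toward complication. Neither is said to prevail. A switch-off with no untoward clinical occurrence is not a reportable event under 11.1 and lies outside the overlap.

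**Step 2. Follow the event to adjudication.** Section 7.5 names two inputs to the CEC: complications and treated spontaneous episodes. No section describes review of events that a site has called observations. Section 19.1 could cover them as relevant adverse events, but it does not say who decides relevance.

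**Step 3. How close must the result be for this to matter?** The plan's sample-size parameters are redacted, so there is no stated figure to reproduce. From the documents: goal 0.85, one-sided 95% bound (z = 1.645), Peto standard error, enrolment target 1,616. Assumed: n = 700 to 1,100 at risk at day 1800.

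The smallest estimate S that passes solves S − 1.645 × S × √((1 − S)/n) = 0.85.

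- n = 700: S = 0.8695. Check: 0.8695 − 1.645 × 0.8695 × √(0.1305/700) = 0.8695 − 0.0195 = 0.850.
- n = 900: S = 0.8673.
- n = 1,100: S = 0.8657.

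**Step 4. What does one misfiled event do?** Ignoring censoring, one event in 1,616 moves the rate by 1/1,616 = 0.06 percentage points, and ten events move it by 0.62. Late events weigh more because a Kaplan-Meier step is about S/n at the time of the event. Ten late events with an assumed 1,000 at risk and S near 0.87 would move it by about 10 × 0.87/1,000 = 0.87 points.

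**Step 5. Illustrate the effect on the test.** If a share f of Type I complications is misfiled, the counted rate is 1 − (1 − true rate) × (1 − f). The chance of passing below uses a normal approximation.

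- True rate 85.0%, f = 0: about 6% with 700 or 1,000 at risk. This is slightly above 5% because the Peto standard error shrinks as S rises.
- True rate 85.0%, f = 5%: counted rate 1 − 0.15 × 0.95 = 85.75%. The chance of passing is 16% with 700 at risk and 19% with 1,000. Without censoring, this is about 12 of 242 events (0.15 × 1,616 = 242; 0.05 × 242 = 12).
- True rate 83.0%, f = 10%: counted rate 1 − 0.17 × 0.90 = 84.7%. The chance of passing is 3% to 4%.

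The documents give no expected value of f. These figures show sensitivity and are not a forecast.

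**The case against.** The strongest reply is that the endpoint does not use the observation label. Sections 6.1 and 10.1 define a Type I complication by outcome, and their footnotes expressly include a generator programmed permanently off. Read correctly, the plan counts the event whatever other definition it meets. This stands: the risk is misclassification in practice, not exclusion by rule.

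A reader might infer that only site-labelled complications reach the CEC and that the rest are never counted. The documents do not support that. Section 7.5 also sends treated episodes, calls the site classification preliminary, and does not say that the site label decides what is forwarded. Section 19.1 is broader, and the charter is not among the documents.

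Deaths are the weak part of the concern. They are reported within 2 working days (Table 12), and 11.3 calls for device interrogation and a death letter. All-cause mortality is analysed separately (6.6). A device-caused death is unlikely to remain unnoticed as an observation.

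Switch-offs also leave traces. Visits with a programming change are submitted with summary reports (7.2.9, 7.2.10), system parameters are collected from implant onward (Table 2), and a device removed from service needs a status form (7.3). The sponsor can therefore see the data. No section, however, says that these records are used to re-examine the observation label or to trigger adjudication.

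**Conclusion.** The overlap is real and follows from the definitions alone. It is most plausible for a Type I event that ends with the generator permanently off and no surgery, and much less so for deaths. The endpoint wording gives the right answer. The sorting rule and the reprogramming example can lead a site to the wrong one, and the documents show no defined step that would correct it. Uncorrected errors of this kind favour the 85% goal.

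The size is unknown. It depends on how many Type I events fall in the overlap and how many are mislabelled, and the documents give neither. The thresholds of about 86.6% to 87.0% rest on the assumed number at risk. A few misfiled events would change the conclusion only if the result lay close to that threshold, and nothing in the documents shows that it will. This is an inexpensive correction to a primary-endpoint definition, not evidence that the endpoint is biased.

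**What to change.** 1. In 11.2 and Appendix A, define an observation as an adverse event that is not a complication. Limit the reprogramming example to changes that leave device function intact.
2. In 11.3, replace sorting by the intervention required with sorting by the complication definition.
3. In 7.5, state that the CEC reviews all deaths and all reported adverse events in which the generator is programmed off, whatever category or type the site assigned. Type must be included because a site that assigns another type would also take the event out of the primary endpoint.

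The cost is wording in a few places and a few more cases for an existing committee. The reported rate may be slightly less favourable. The change affects only how events are classified and adjudicated, not how subjects are treated.

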11.3 Classification of Adverse events

All adverse events will be categorized as observations or complications based on the intervention required to resolve the adverse event. A complication is an adverse event that results in permanent loss of device function, invasive intervention or death.

All adverse events will also be classified by type based on the cause of the adverse event. The following definitions for adverse event types will be used:

- Type I: Caused by a component of the S-ICD System, including the pulse generator, electrode, electrode insertion tool or programmer

³¹ *Permanent loss of device function* refers to: 1) the permanent loss of shock therapy and/or post shock pacing; 2) permanent loss of appropriate sensing in all available sensing configurations (oversensing that results in persistent inappropriate shocks or undersensing that could lead to undetected arrhythmias). Loss of device function includes programming the PG permanently off or temporarily off in advance of an explant/revision.

- Type II: Other adverse events not specifically caused by a component of the S-ICD System, but would not have occurred in the absence of the implanted S-ICD System
- Type III: Caused by a change in the subject's condition
- Type IV: Pre-existing medical condition or occurred while the subject was not enrolled

Adverse events will typically be labelled and categorized according to the clinical presentation, including device malfunctions.

In the event of a subject death, the S-ICD System should be interrogated, removed from the subject, and returned to BSC for analysis. The data related to the death should be recorded in the database in a timely fashion. A detailed death letter should also be provided to the sponsor.

In the event that the SQ-RX pulse generator or Q-TRAK subcutaneous electrode cannot be removed, the SQ-RX pulse generator should be interrogated prior to interment. Note that failure to remove the S-ICD System from a deceased subject prior to cremation may cause the battery to explode when the device is exposed to extreme temperatures.

All subject deaths will be reported by the sponsor to the appropriate regulatory agencies.

